7.1 DEMOGRAPHIC AND OTHER BASELINE CHARACTERISTICS

Only descriptive statistics are planned for this section of the report, for the RS of patients.

7.2 CONCOMITANT DISEASES AND MEDICATION

Only descriptive statistics are planned for this section of the report, for the RS of patients.

Concomitant diseases will be coded using the most current version of Medical Dictionary for Regulatory Activities (MedDRA) and will be summarised by primary system organ class (SOC) and preferred term (PT). Concomitant medications will be coded using the most current version of WHO-DD and will be summarised by ATC3 class and PT. In situations where a therapy belongs to more than one ATC3 class all classes will be presented, along with explanatory footnotes. Separate summaries of concomitant medications started prior to and during the period of taking study medication will be produced.

7.3 TREATMENT COMPLIANCE

Only descriptive statistics are planned for this section of the report, for the TS of patients. Appropriate summaries of compliance before and from the start of the COVID-19 disruption will also be produced.

7.4 PRIMARY ENDPOINT

The primary endpoint of PFS as assessed by blinded independent assessment will be analysed using the RS of patients.

[figure not shown]
7.4.1 Primary analysis of the primary endpoint

[figure not shown]
The primary endpoint will be analysed using a stratified (presence of baseline bone-only metastases, prior CDK4/6 inhibitor treatment, menopause status) log-rank test to assess the effect of treatment.

A stratified Cox proportional hazards model will be used to estimate the HR of the treatment effect and the corresponding asymptotic two-sided 95% Wald CI. A HR of less than one will favour the xentuzumab arm. Breslow's method for handling ties will be used.

Kaplan-Meier (KM) estimates will be used to display the distribution of PFS for each treatment group on a KM curve. To support the plot, estimated survival probabilities at specific time points of interest (scheduled imaging time-points) will be tabulated along with 95% CIs, using Greenwood's variance estimate. In addition, the survival distribution will be used to provide estimates of the median, 25th and 75th percentiles.

Suitable methods will be used to check the assumption of proportional hazards.

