7 STATISTICAL METHODS AND DETERMINATION OF SAMPLE SIZE

7.1 STATISTICAL DESIGN - MODEL

This is a randomised, double-blind, placebo-controlled multi-centre trial in women with HR+/HER2- advanced or metastatic breast cancer with non-visceral disease. The primary objective of the trial is to evaluate whether xentuzumab in combination with everolimus and exemestane prolongs PFS, independently assessed according to RECIST 1.1, in comparison to everolimus and exemestane alone.

Based upon these design considerations, treatment groups will be compared for the primary endpoint via a stratified log-rank test, stratified by the presence of baseline bone-only metastases (Yes/No), prior CDK4/6 inhibitor treatment (Yes/No) and menopause status (pre/post).

If the criterion for the seamless option is met then this Phase II trial will be expanded into a confirmatory Phase III trial, similar to the 2-in-1 design outlined in [R18-2061](#). Pertinent detail regarding hypothesis testing, alpha-spending/control along with increases in sample size in the expansion scenario has been detailed in the following sections. However, prior to expanding the trial additional detail will be provided via a formal protocol amendment.

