7.2 NULL AND ALTERNATIVE HYPOTHESES

If at the time-point of the primary PFS analysis for this Phase II trial the hazard ratio (using the model defined in [Section 7.3.1](#)) is below a pre-defined criterion (to be defined in the DMC charter, prior to trial initiation), in favour of the xentuzumab arm, then the trial will be expanded into a confirmatory Phase III trial. No formal hypothesis testing will be performed if the trial is not expanded.

However, if the trial is expanded, formally, the null hypothesis for the primary PFS endpoint at the end of Phase III is:

$$H_0: S_{PFS; xentuzumab}(t) \leq S_{PFS; control}(t), \text{ for all } t > 0,$$

versus the alternative hypothesis:

$$H_1: S_{PFS; xentuzumab}(t) > S_{PFS; control}(t), \text{ for any } t > 0,$$

where $S_{PFS}(t)$ is the probability that a patient passes time t without experiencing a PFS event.

The expanded study will be considered positive if the null hypothesis for the primary endpoint can be rejected.

Also in the expanded trial scenario, for the secondary OS endpoint, the null hypothesis is:

$$H_0: S_{OS; xentuzumab}(t) \leq S_{OS; control}(t), \text{ for all } t > 0,$$

versus the alternative hypothesis:

$$H_1: S_{OS; xentuzumab}(t) > S_{OS; control}(t), \text{ for any } t > 0,$$

where $S_{os}(t)$ is the probability that a patient passes time t without experiencing an OS event.

The hypothesis testing will be performed on all randomised patients. The testing strategy includes the endpoints PFS and OS, tested in a hierarchical manner, and will control the overall type-1 error rate at a level of 0.025 (one-sided).

If the trial is expanded then the primary PFS analysis at the end of Phase II will be considered as an interim analysis. Refer to [Section 7.4](#) for further details on this planned interim analysis and the control of the type I error rate in the situation where the trial is expanded.

Superiority, for the endpoint of interest will be declared if the related null hypothesis is rejected in favour of the alternative at the defined significance level and the estimated hazard ratio of xentuzumab vs. control is <1 .

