The primary efficacy analyses will be performed on the randomised set (RS), consisting of all randomised patients. Patients randomised and not treated will be analysed according to the censoring rules defined in [Section 7.5](#). Randomised patients who receive the wrong treatment will be analysed according to their planned randomised treatment group. No per-protocol analysis is planned.

Stratification (where stated) of analyses will be based on the presence of baseline bone-only metastases (Yes/No), prior CDK4/6 inhibitor treatment (Yes/No) and menopause status (pre/post). Refer to [Section 7.6](#) for further details on the randomisation stratification factors.

The safety analysis will be based on the treated set (TS), consisting of all patients treated with at least one dose of any study treatment. Patients will be analysed according to the actual treatment received.

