7.6 RANDOMISATION

Patients will be randomised in blocks to double-blind treatment with a 1:1 ratio (xentuzumab in combination with everolimus and exemestane: everolimus and exemestane alone).

Randomisation will be stratified by the following factors:

- Presence of baseline bone-only metastases (Yes, No)
- Prior CDK4/6 inhibitor treatment (Yes/No)

BI will arrange for the packaging and labelling of trial medication. The randomisation list will be generated using a validated system, which involves a pseudo-random number generator so that the resulting treatment will be both reproducible and non-predictable.

The block size will be documented in the CTR. Access to the codes will be controlled and documented.

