7.7 DETERMINATION OF SAMPLE SIZE

For the primary endpoint of PFS, it is assumed that xentuzumab in combination with everolimus and exemestane will increase the median from 9.9 months ([R16-0802](#)) in the everolimus and exemestane alone group to 19.8 months. Assuming an exponential distribution, this is equivalent to a reduction in the risk for progression of disease or death of 50%, corresponding to an underlying hazard ratio (HR) of 0.50. With 80 eligible patients randomised over a 15 month period, 40 PFS events are predicted to be reached on average around 30 months after the first patient is randomised. This assumes approximately 20% of patients randomised will either drop out of the trial without evidence of disease progression or be assessed as non-PD by independent assessment when the investigator assigned disease progression. If this proportion differs significantly from the 20% assumed then the number of patients randomised may be increased in order to observe 40 PFS events in a timely manner, but the number of patients randomised will not exceed 100 patients.

[Table 7.7: 1](#) shows the probability of observing various HR thresholds for different underlying (true) HR values and accrued PFS events.

Table 7.7: 1 Probability (%) of observed HR for a range of underlying HRs and PFS event numbers

PFS Events	Underlying (True) HR	Probability ¹ observing HR			
		≤0.50	≤0.60	≤0.75	>0.75
50	HR=1.00	0.7%	3.5%	15.5%	84.5%
40		1.4%	5.3%	18.1%	81.9%
30		2.9%	8.1%	21.5%	78.5%
50	HR=0.60	26.0%	50.0%	78.5%	21.5%
40		28.2%	50.0%	76.0%	24.0%
30		30.9%	50.0%	72.9%	27.1%
50	HR=0.50	50.0%	74.0%	92.4%	7.6%
40		50.0%	71.8%	90.0%	10.0%
30		50.0%	69.1%	86.7%	13.3%
50	HR=0.40	78.5%	92.4%	98.7%	1.3%
40		76.0%	90.0%	97.7%	2.3%
30		72.9%	86.7%	95.7%	4.3%

¹ Calculated using the approximate normal distribution of the estimated log HR

With 40 PFS events, if the underlying HR is 0.50, the chance of observing a treatment effect with HR of ≤0.60 is 71.8%, while the chance of observing a treatment effect with HR of ≤0.75 is 90.0%. Also, if the underlying HR is 1.0, the chance of observing a treatment effect with HR of ≤0.60 is 5.3%, while the chance of observing a treatment effect with HR of ≤0.75 is 18.1%. If the PFS events were increased from 40 to 50, the probability of observing a treatment effect with HR of ≤0.60 is increased by 2.2% (from 71.8% to 74.0%) for an underlying HR of 0.50, similarly for a treatment effect with HR of ≤0.75 the increase in probability is 2.4%.

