Rationale for change		To reflect changes in archival tissues collection as per inclusion criteria 3 as no longer mandatory

Section to be changed		6.2.1 Screening
Description of change		Language regarding provision of archival tissue updated.
Rationale for change		To reflect changes in archival tissues collection as per inclusion criteria 3 as no longer mandatory

Section to be changed		7.1 Statistical Design
Description of change		Removal of post-menopausal term from title Addition of menopause status (pre/post) as a stratification factor for analysis
Rationale for change		Premenopausal women on ovarian suppression will be included in the trial according to adapted inclusion 7.

Section to be changed		7.3 Planned Analyses
Description of change		Change of expected timeframe for PFS analysis from 18 to 15 months. Addition of menopause status (pre/post) as a stratification factor for analysis
Rationale for change		Confirmation of adjusted timelines Inclusion of premenopausal women on ovarian suppression

Section to be changed		7.3.1 Primary endpoint analysis
Description of change		Addition of menopause status (pre/post) as a stratification factor for analysis
Rationale for change		Premenopausal women on ovarian suppression will be included in the trial according to adapted inclusion 7.

Section to be changed		7.4 Interim Analysis
Description of change		Updated predicted timelines for PFS events to 30 months.
Rationale for change		Confirmation of adjusted timelines.

Section to be changed		7.7 Determination of sample size
Description of change		Revised recruitment and event predicted timelines
Rationale for change		Confirmation of adjusted timelines.

11.4 GLOBAL AMENDMENT 4

Date of amendment		05 Feb 2020
EudraCT number		2017-003131-11
EU number		
BI Trial number		1280-0022
BI Investigational Product(s)		Xentuzumab (BI 836845)
Title of protocol		Xenera™ 1: A multi-centre, double-blind, placebo- controlled, randomised phase II trial to compare efficacy of xentuzumab in combination with everolimus and exemestane versus everolimus and exemestane in women with HR+ / HER2- metastatic breast cancer and non-visceral disease
Global amendment due to urgent safety reasons		
Global amendment		X
Section to be changed		Protocol Synopsis-Number of patients entered
Description of change		Approximately added

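### Does the eight-stratum PFS model make the planning probabilities in Protocol Table 7.7: 1 misleading?

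*SAP*

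**What the plan says.** Protocol 7.6 introduces the randomisation factors with "Randomisation will be stratified by the following factors" and lists two: bone-only metastases and prior CDK4/6 inhibitor treatment. Protocol 7.1 stratifies the primary log-rank test by three, ending with "prior CDK4/6 inhibitor treatment (Yes/No) and menopause status (pre/post"), and Protocol 7.3 repeats this. SAP 7.4.1 specifies a "stratified (presence of baseline bone-only metastases, prior CDK4/6 inhibitor treatment, menopause status) log-rank test" and applies the same three factors to the Cox model.

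The third factor came with Global Amendment 3, which made premenopausal women on ovarian suppression eligible and records "Addition of menopause status (pre/post) as a stratification factor for analysis".

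Protocol 7.2 defines the quantity that decides expansion as "the hazard ratio (using the model defined in" Section 7.3.1, which is the stratified Cox model. Table 7.7: 1 gives the chance of seeing various HRs at 30, 40 and 50 events. Its footnote reads "Calculated using the approximate normal distribution of the estimated log HR" and does not mention strata.

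**The concern.** Three binary factors make eight cells. With 80 patients and 40 events, a cell holds on average 80/8 = 10 patients and 40/8 = 5 events. If 10% of patients were premenopausal, the four premenopausal cells would share 8 patients, about two each. In a stratified model an event adds nothing once only one arm remains at risk in its cell, so sparse cells waste events.

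The sponsor judged 40 events sufficient from Table 7.7: 1. If that table assumes more information than the planned model delivers, the chance of a falsely promising HR is understated and the chance of detecting a true HR of 0.50 is overstated. The protocol itself weighs differences of this order: for 50 events against 40 it reports that "the probability of observing a treatment effect with HR of ≤0.60 is increased by 2.2" percentage points. It is also natural to ask why a factor that did not constrain randomisation should define strata in the analysis.

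**Working it through.** **1. Reproduce the table.** Take P(observed HR ≤ t) = Φ((ln t − ln HR)/SE), with SE = 2/√events. For 40 events, SE = 2/√40 = 0.316.

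- True HR 1, t = 0.60: Φ(−0.511/0.316) = Φ(−1.62) = 5.3%
- True HR 0.50, t = 0.60: Φ(0.182/0.316) = Φ(0.58) = 71.8%
- True HR 0.50, t = 0.75: Φ(0.405/0.316) = Φ(1.28) = 90.0%

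These are the printed values, and all twelve rows reproduce. The table is correct for its formula, which is the unstratified one.

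**2. Information per event.** Near HR 1, an event in a cell where a proportion p of those at risk are on xentuzumab counts as 4p(1−p) effective events. That is 1 for a balanced risk set, 4 × 2/3 × 1/3 = 0.89 for 2:1, 0.75 for 3:1, and 0 with one arm left.

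**3. Simulate the planned model.** Inputs from the documents:

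- Protocol 7.7: 80 patients, 15 months of accrual, control median 9.9 months, cut at 40 events, about 20% dropout (15–23% lost by the cut in the simulation).
- Flow Chart: scan windows.
- SAP 7.4.1: Breslow ties.
- Protocol 1.3: bone-only share 16/33, from trial 1280.4.

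Assumed, because the documents do not say: premenopausal share 5–30%, prior CDK4/6 share 30–70%, blocks of four, and prognostic HRs of 0.8 (bone-only), 1.25 (prior CDK4/6) and 1.2 (premenopausal). There were 40,000 trials per scenario.

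Effective events at true HR 1 were 36.8–37.0 with the four randomisation cells. With eight cells they were 35.3 (5% premenopausal) falling to 32.8 (30%). Menopause status therefore costs 1.7–4.0 events.

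| Probability, % | Printed, 40 events | No strata | 4 strata | 8 strata | Printed, 30 events |
|---|---|---|---|---|---|
| True HR 1, observed ≤0.60 | 5.3 | 5.3–5.6 | 6.0–6.3 | 6.4–7.4 | 8.1 |
| True HR 0.50, observed ≤0.60 | 71.8 | 70.1–71.0 | 70.1–71.1 | 69.3–70.8 | 69.1 |
| True HR 0.50, observed ≤0.75 | 90.0 | 88.9–89.4 | 88.6–89.0 | 87.3–88.4 | 86.7 |

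Monte Carlo error (95%) is about ±0.25 points at 7%, ±0.45 at 70% and ±0.32 at 88%. The formula in step 1 with 33 events gives 7.1%, 70.0% and 87.8%, in line with the eight-stratum column. A simpler simulation with exact event times gave 6.8–7.5%, 69.8–70.9% and 88.0–88.7%.

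**4. Attribute the gap.**

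- At true HR 1, the unstratified model matches the table, so the rise of 1.1–2.1 points is nearly all stratification.
- At true HR 0.50, the unstratified model already falls short, by 0.8–1.7 points for ≤0.60 and 0.6–1.1 for ≤0.75. That part comes from the normal approximation. Going from four to eight cells adds 0.3–1.1 and 0.4–1.3 points.

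**5. Precision and centring.** The standard deviation of the log HR is 1.02–1.07 times that with four strata. In the exact-time simulation, with no prognostic effects, the eight-stratum median HR was 0.498 at a true 0.50.

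**6. What dropping the factor would do.** If menopause status were strongly prognostic (HR 2), P(≤0.60) at true HR 0.50 would be 69.7–70.4% with eight strata and 68.1–70.1% with four. The four-stratum median HR would drift to 0.505–0.514. In that case the planned model does at least as well.

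**The case for a change.** The best case for acting is the null row. Going from 5.3% to 6.4–7.4% is a relative increase of 1.1/5.3 = 21% to 2.1/5.3 = 40% in the chance of a falsely promising HR. The SAP covers only the non-expanded case, in which no formal test is made, so the HR and its interval are the main result, and that interval is 2–7% wider on the log scale than with the randomisation strata. A footnote and two extra Cox runs would cost almost nothing.

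The direction of the effect and the null-case figures stand. The rest is weaker:

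- Setting the whole shift at true HR 0.50 beside the 2.2- and 2.4-point gains for 50 events credits menopause status with losses it does not cause. Its own share is at most about half of those gains.
- A footnote giving an event equivalent would put into the protocol a number that depends on an unknown premenopausal share; the loss tends to zero as that share does. These women became eligible only with Amendment 3.
- An HR stratified by the two randomisation factors would be post hoc now that the trial is unblinded. It may also already be planned: the SAP contents show a redacted block directly after 7.4.1, so its absence cannot be claimed.

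**Conclusion.** No change is needed. The table is labelled as approximate, and its 30- and 40-event rows bracket every eight-stratum value, so a reader can already see what a loss of this size means. Stratifying by menopause status is a fair trade-off: a loss of 1.7–4.0 effective events out of about 37, in exchange for protection if the newly admitted premenopausal patients have a different prognosis. The choice is pre-specified, and the probabilities at true HR 0.50 stay near 70% and 88%, so the Protocol 7.7 judgement that 40 events allow an informed decision is not overturned. Protocol 1.4 reports that the primary analysis is complete and showed no added benefit, so revising the planning table would alter no decision still to be made.

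These sizes rest on the assumed stratum shares, block size and prognostic effects. The actual expansion threshold is in the DMC charter, which is not available; 0.60 and 0.75 are only the values the table displays. A remark that the table ignores stratification, or a labelled sensitivity HR on the two randomisation factors, would be harmless but is optional.

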7.5 SECONDARY ENDPOINTS

7.5.1 Key secondary endpoints

This section is not applicable, as no key secondary endpoint has been specified in the protocol.

7.5.2 Secondary endpoints

Overall survival

The analysis of this endpoint will follow that of the primary endpoint, detailed in [Section 7.4.1](#).

Disease control

A logistic regression model adjusting for the previously defined stratification factors will be used for the analysis of this binary endpoint. The treatment groups will be compared via the likelihood ratio test and presented along with the corresponding odds ratio and 95% CI. An odds ratio greater than one will favour the xentuzumab arm.

Duration of disease control

[figure not shown]
KM estimates will be calculated for each treatment group to provide estimates of the median, 25th and 75th percentiles and their corresponding 95% CIs.

[figure not shown]
Objective response

OR will be analysed as for DC above.

Time to pain progression or intensification of pain palliation

The analysis of this endpoint will follow that of the primary endpoint, detailed in Section 7.4.1.

7.7 EXTENT OF EXPOSURE

A descriptive summary of total duration of study treatment will be produced both for the combined treatment and for each of the individual components. A dose reduction summary of everolimus will also be produced along with dose intensity summaries for each of the individual components of the study treatment. Refer to [Section 5.4.2](#) for further details.

A Kaplan-Meier plot of the time to permanent discontinuation of all study medication (date of last administration of study medication – date of first administration of study medication + 1) will also be produced by treatment group. Patients who have not permanently discontinued study medication will be censored at the date of the snapshot for the analysis.

Appropriate summaries of exposure before and from the start of the COVID-19 disruption will also be produced.

7.8 SAFETY ANALYSIS

All safety analyses will be performed on the treated set. In addition to the summaries described below, standard tables required for the clinical trials disclosure process (ClinicalTrials.gov and EudraCT) will be produced [\(4\)](#).

7.8.1 Adverse Events

AEs will be coded with the most recent version of the MedDRA. The severity of AEs will be scaled according to Common Terminology Criteria (CTC) AE version 5.

Unless otherwise specified, the analyses of AEs will be descriptive in nature. All analyses of AEs will be based on the number of patients with AEs and not on the number of AEs.

For analysis, multiple AE occurrence data on the eCRF will be collapsed into an AE if all of the following applies:

- All AE attributes are identical (Lowest Level Term [LLT], CTCAE grade, action taken with trial medication, therapy required, seriousness, reason for seriousness, relationship, outcome, AE of special interest)
- The occurrences are time overlapping or time-adjacent (time-adjacency of 2 occurrences is given if the second occurrence started on the same day or on the day after the end of the first occurrence).

For further details on the analysis and presentation of AE data refer to BI standards [\(5\)](#).

The analysis of AEs will be based on the concept of treatment emergent adverse events. That means that all AEs with an onset between first drug intake and last drug intake + REP (42 days) will be assigned to the randomised treatment. All AEs with an onset before first drug intake will be assigned to 'screening' and all AEs with an onset after the residual effect period will be assigned to 'post-treatment' (for listings only). For details on the treatment definition, see [Section 6.1](#).

An overall summary of AEs will be presented; along with the standard categories presented additional categories for action taken and drug relationship with each compound, worst CTCAE grade and infusion related reaction response. The frequency of patients with AEs will be summarised by treatment, highest CTCAE grade, primary SOC and PT. The SOC's will be sorted alphabetically; PT's will be sorted by decreasing frequency (within SOC). Only AEs with a given CTCAE grade will be displayed in tables showing AEs by worst CTCAE grade. AEs with a missing CTCAE grade will not be displayed in these tables; a footnote will explain that these AEs are not included and a separate listing of them will be produced if required. The following tables will be produced for AEs during the on-treatment period:

- Patients with AEs
- Patients with any related AE

- Patients with related xentuzumab/placebo AEs
- Patients with related everolimus AEs
- Patients with related exemestane AEs
- Patients with SAEs
- Patients with related xentuzumab/placebo SAEs
- Patients with related everolimus SAEs
- Patients with related exemestane SAEs
- Patients with other significant AEs, defined as serious and non-serious AEs that lead to dose reduction or permanent discontinuation of any study medication
- Patients with AEs leading to death (no CTCAE grade required)
- Patients with AEs leading to discontinuation of xentuzumab/placebo
- Patients with AEs leading to discontinuation of everolimus
- Patients with AEs leading to discontinuation of exemestane
- Patients with AEs leading to dose reduction of everolimus
- Patients with AEs leading to dose interruption of xentuzumab/placebo
- Patients with AEs of Special Interest (refer to Section 5.2.6.1 of the CTP)

In addition some AEs are considered to be of particular importance and special search categories (SSC) of groupings of PTs based on Standardised MedDRA Queries (SMQ), BI customised MedDRA Queries (BIcMQ) or MedDRA High Level Terms (HLT) are defined at the project level, the latest version of which will be used. Details of the current version are provided in the Table 7.8.1: 1 below.

SSCs summaries of patients with AEs and related AEs by treatment, highest CTCAE grade, grouped term and PT will be produced. Similar summaries will be produced for the BIcMQ SARS-COV-2-infections.

Table 7.8.1: 1 Overview of Special Search Categories

Grouped term	Groupings
Hepatic impairment	SMQ: Drug related hepatic disorders – comprehensive search
Hyperglycaemia narrow	SMQ: Hyperglycaemia / new onset diabetes mellitus (narrow terms only)
Infusion related reaction	SMQ: Hypersensitivity
Non-infectious pneumonitis	SMQ: Interstitial lung disease (narrow terms only)
Renal insufficiency	SMQ: Acute renal failure, SMQ: Proteinuria, HLT: Glomerulonephritis and nephrotic syndrome
Weight loss	BIcMQ: Weight loss
Neutropenia	SMQ: Haematopoietic leukopenia (narrow terms only)
Stomatitis	BIcMQ: Gastrointestinal mucositis (subsearch1: Stomatitis)

Table 7.8.1: 1 Overview of Special Search Categories (cont.)

Grouped term	Groupings
Asthenia	MedDRA PTs of Asthenia, Fatigue, Lethargy, Malaise, and Decreased activity
Haemorrhage	SMQ: Haemorrhage laboratory terms (narrow terms only), SMQ: Haemorrhage terms (excl. laboratory terms)
Anemia	SMQ: Haematopoietic erythropenia
Thrombocytopenia	SMQ: Haematopoietic thrombocytopenia (narrow terms only)
Thromboembolism	SMQ: Embolic and thrombotic, vessel type unspecified and mixed arterial and venous
Bradycardia	SMQ: Torsade de pointes/QT prolongation, PT of Bradycardia
Rash	BIcMQ: Skin eruptions (subsearch2: Skin rash potentially related to drug use)

